### 11.3 Phase II

#### Primary Objective:

Once a recommended dose has been determined in the Phase I portion of the study, the cohort will be expanded so that 36 new patients will be treated at this dose level. The primary objective of this phase is to evaluate the safety and efficacy of the combination of entinostat and IL-2. The primary endpoint is overall response rate (complete plus partial). Enrollment is expected to be

between 1 and 2 patients per month. The combination treatment will be considered unsuccessful if the response rate is 20% or less, and it will be considered active enough to pursue further if the response rate was 40% or greater. To test this hypothesis, the fixed sample size for a single-stage study with a type I error of 10% and a type II error of 10%, based on an exact binomial test, is 36. If 11 or more of the patients have a response, the hypothesis that the response rate is  $\leq 20\%$  is rejected with a target error rate of 0.10. This design has type I and type II errors of 0.09 and 0.09, respectively.

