#### Secondary Objectives:

Secondary endpoints will be used to determine the effect of entinostat on progression free survival (PFS), survival, time-to tumor progression and parameters measuring immune response.

Failure rates will be used to compare the PFS, overall survival and time-to-tumor progression of metastatic RCC patients treated with high dose aldesleukin combined with entinostat to the historical failure rates of patients treated with high dose aldesleukin alone. The failure rate is estimated by dividing the number of events ( $d$ ) by the sum of the exposure time in the study

cohort:  $\lambda = d / \sum t_i$ . The 95% confidence interval is calculated as:  $\lambda \pm Z_{1-\alpha/2} \frac{\lambda}{\sqrt{d}}$ .

The historical PFS failure rate observed in the randomized trial of IL-2 reported by the Cytokine Working Group was 2.77 per person year (median PFS of 3 months). Patients eligible for this study are expected to be homogenous group with comparable prognostic characteristics. Enrollment is expected to be between 1 and 2 patients per month with an accrual period of 6 years and 12 months of follow-up. With a total of 34 events in 36 patients, the study would yield 79% power to detect a decrease in the PFS failure rate to 1.85 per person year of follow-up (an increase of 1.5 months in the median PFS compared to the historical median) at an alpha level of 0.1 (one-sided).

We do not expect that different doses of entinostat during the period off aldesleukin (maintenance) will affect the primary endpoint since objective responses have been rarely observed with single agent entinostat. We expect that the vast majority of patients will be able to tolerate the 10 mg maintenance dose if the phase II recommended dose in combination with aldesleukin is 5 mg. Should we observe discrepancies in the maintenance dose level of entinostat we will consider subgroup analysis to determine the secondary objective PFS in the different group of patients.

The toxicity of IL-2 when combined with entinostat will be further characterized following the phase II portion of this study. The exact binomial proportion for prolonged grade 4 toxicities with the 95% confidence interval will be given. Additional toxicity frequencies, proportions, and 95% CIs will be given by type and grade of toxicity.

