#### 11.4 Toxicity monitoring

A sequential probability ratio test (SPRT) will be used to provide a monitoring boundary for stopping the study in case there is moderate evidence that the proportion of extended grade 4 toxicities is 20% as opposed to the permitted rate of 5%. This monitoring boundary will be used to evaluate the toxicity data after every patient. The SPRT is based on testing two simple hypotheses on the basis of the likelihood ratio. The likelihood function for a binary toxicity outcome is binomial and the log likelihood ratio will be used to determine the relative evidence in favor of two hypothesized prolonged grade 4 toxicity rates,  $p_1=0.2$  and  $p_2=0.05$ . The

likelihood ratio is:

$$\text{Likelihood ratio (For } p_1 \text{ vs } p_2 \mid \text{Data)} = \frac{\Pr(\text{data} \mid \theta = 0.2)}{\Pr(\text{data} \mid \theta = 0.05)} = \frac{\theta^x (1 - \theta)^{N-x}}{\theta^x (1 - \theta)^{N-x}}$$

where  $N=36$  and  $x$  is the number of toxicities observed. We will stop the study if there is moderate evidence,  $LR \geq 8.0$ , that the proportion of prolonged grade 4 toxicities is 20% versus 5%. The stopping boundary corresponding to this LR is given below. If the number of toxicities falls above the line any point along the study, the study will be stopped. Table 1 gives the observed number of prolonged toxicities for which this boundary would be crossed after each patient accrued ( $N$ ). The rate of erroneously stopping the study using this boundary is approximately  $1/8$  or  $0.125$ .

[figure not shown]

Table 1. Observed number of prolonged toxicities (Tox) where SPRT boundary would be crossed after each patient accrued ( $N$ ).

N	1	2	3	4	5	6	7	8	9	10	11	12	13	14	15	16	17	18
Tox	2	2	2	2	2	2	3	3	3	3	3	3	3	3	3	4	4	4

N	19	20	21	22	23	24	25	26	27	28	29	30	31	32	33	34	35	36
Tox	4	4	4	4	4	4	5	5	5	5	5	5	5	5	5	6	6	6

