## **11.7 Reporting and Exclusion**

### **11.7.1 Evaluation of toxicity**

All patients will be evaluable for toxicity from the time of their first dose of entinostat

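### Section 11.3 reports the prolonged grade 4 toxicity rate with a fixed-sample exact 95% interval although section 11.4 can stop the study on that same count; the rate is biased upward on average, and the lower limit is too high too often near the permitted 5%

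*Combined protocol and SAP*

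**What the plan says.** Under Secondary Objectives, section 11.3 states how the toxicity result of Phase II will be reported: "The exact binomial proportion for prolonged grade 4 toxicities with the 95% confidence interval will be given". The planned maximum is 36 patients ("36 new patients will be treated at this dose level"), and under 11.7.1 every patient counts for toxicity from the first entinostat dose.

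Section 11.4 monitors the same endpoint with a sequential probability ratio test that contrasts a 20% rate with a permitted 5% and stops at a likelihood ratio of 8 or more. On timing: "This monitoring boundary will be used to evaluate the toxicity data after every patient". On consequence: "If the number of toxicities falls above the line any point along the study, the study will be stopped". Table 1 lists the count that triggers a stop at each N from 1 to 36. There is no lower boundary.

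Sections 11.3, 11.4 and 11.7 contain no estimate or interval that allows for this rule, and nothing says that the 11.3 figures are unadjusted for it.

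**The concern.** An exact binomial interval takes N as fixed in advance. Here N is set by the toxicity outcomes themselves: the study ends at the first N where the count reaches Table 1, which favours moments just after a cluster of events. The raw x/N then overstates the true rate on average, and the tail probabilities of the interval are not those of a fixed sample.

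Toxicity is part of the Phase II primary objective (1.2.1, 11.3) and is a secondary objective (1.3.2). If the boundary is crossed, this rate becomes the main safety result, and readers will set its interval against the plan's own 5% and 20% benchmarks. The question is about the reported estimate, not about the boundary or the decision to stop.

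**Working it through.** **Inputs.** Rates 0.20 and 0.05, threshold 8, a look after every patient (11.4); maximum N = 36 (11.3). Assumption: each patient's outcome is known before the next look.

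**Step 1: reproduce Table 1.** The boundary is the smallest x with x·ln(0.20/0.05) + (N − x)·ln(0.80/0.95) ≥ ln 8, that is 1.3863x − 0.1719(N − x) ≥ 2.0794. At N = 6, x = 2 gives 2.085, which crosses; at N = 7, x = 2 gives 1.913, which does not, so 3 events are needed. Continuing gives 2 (N 1–6), 3 (7–15), 4 (16–24), 5 (25–33) and 6 (34–36). All 36 entries match Table 1.

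**Step 2: list the end points.** A crossing is impossible at N = 1, 7, 16, 25 and 34, which leaves 36 − 5 = 31 stopping points. Six completed outcomes (0 to 5 events in 36) bring the total to 37.

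**Step 3: bias of x/N.** An exact forward recursion over all paths gives:

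| True rate | P(stop) | Mean x/N | Mean of median-unbiased estimate |
|---|---|---|---|
| 5% | 0.074 | 6.6% | 6.7% |
| 10% | 0.348 | 15.4% | 13.8% |
| 15% | 0.667 | 24.0% | 20.6% |
| 20% | 0.873 | 31.3% | 26.6% |

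The bias is an average over stopped and completed studies. Among studies that reach 36 patients without crossing, the mean is below the truth (4.5% at a true 5%, 10.2% at 20%).

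**Step 4: lower-tail error at a true 5%.** Add the probabilities of the end points whose ordinary lower limit exceeds 5%:

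- 2 events, N 2–5: 0.0226
- 3 events, N 8–13: 0.0131
- 4 events, N 17–22: 0.0065
- 5 events, N 26–33: 0.0065
- 6 events, N 35–36: 0.0003

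The total is 0.049 (terms rounded), against at most 0.025 nominal and 0.008 with a fixed N of 36. The error exceeds 2.5% for true rates of about 2.7% to 6.75% (and in a sliver near 1.7%), with a maximum of 5.4% at 4.3%.

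**Step 5: limits that use the boundary.** Order the end points from most to least extreme: earlier stops first, then completed studies by falling count. The lower limit is the rate at which the probability of the observed or a more extreme end point is 0.025; the upper limit is the rate at which the probability of a strictly more extreme one is 0.975. The median-unbiased estimate is the midpoint of the two corresponding solutions at 0.5. The UMVUE (uniformly minimum-variance unbiased estimate) is the number of paths to the end point that begin with an event, divided by all paths to it.

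| Result | Raw rate, ordinary 95% CI | Stage-wise 95% CI | Median-unbiased | UMVUE |
|---|---|---|---|---|
| Stop at 3/10 | 30.0% (6.7–65.2) | 4.1–57.0 | 23.3% | 14.3% |
| Stop at 4/20 | 20.0% (5.7–43.7) | 3.4–36.9 | 15.6% | 9.3% |
| Complete, 5/36 | 13.9% (4.7–29.5) | 3.1–26.5 | 12.0% | 7.2% |
| Complete, 3/36 | 8.3% (1.8–22.5) | 1.7–22.2 | 8.5% | 6.3% |

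The ordinary interval excludes 5% at 4 + 6 + 6 + 8 + 2 = 26 of the 31 stopping points. The stage-wise interval does so at 4 (2 events by patient 2, 3, 4 or 5). They disagree at 22. The stage-wise lower-tail error at a true 5% is 0.023.

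**Step 6: outcomes not yet known at a crossing.** The only toxicity window in the protocol is the 45-day DLT window. At 1 to 2 patients per month, 1.5 to 3 patients enter in that time. The 6-year accrual period in 11.3 implies 36/72 = 0.5 per month, or 0.75 patients. If such patients are counted in x/N after a crossing, the lower-tail error at 5% becomes 3.5% with 1 extra patient, 2.5% with 2 and 2.0% with 3. Mean x/N at a true 20% falls from 31.3% to 26.7% with 2 extra.

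**The case against.** A reader might infer that the planned 95% interval is invalid. The calculation does not support that. Its two-sided coverage is 95.1% at a true 5% and never below about 94.6%, because the upper tail misses little or nothing at low rates. Its tail errors equal those of the stage-wise interval at true rates of 10%, 15% and 20%. For stops at patients 2 to 6 the lower limits are identical. So it is also not true that the lower limit is always too high.

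A reader might also infer that one correct answer exists. It does not: at 3/10 the median-unbiased estimate is 23.3% and the UMVUE 14.3%. The median-unbiased estimate does not improve mean bias at 5% and only partly removes it at 20%. Section 11.4 argues in terms of likelihood, under which x/N is the maximum likelihood estimate whatever the stopping rule, and the raw incidence is a plain fact about the treated patients.

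Finally, no decision uses this interval: stopping follows Table 1 and success follows 11 responses in 36. At a true 5% the study crosses in only 7.4% of cases, and overrun dilutes the excess.

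All of this stands and sets the size of the point. It argues for keeping the raw figures and against replacing them. It does not answer the remaining problem, that at 22 of 31 stopping points the unlabelled interval excludes the plan's own permitted rate when one that respects the boundary does not.

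**Conclusion.** The point holds as a reporting weakness. The planned estimate ignores a stopping rule that acts on the same count. Its mean is too high by 1.6 percentage points at a true 5%, 5.4 at 10% and 11.3 at 20%. Lower-tail error is about twice nominal at 5%, and the excess is essentially limited to true rates of about 2.7% to 6.75%. Little changes if the study completes with 0 to 3 events.

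These figures assume that every outcome is known before the next look and that a stop occurs on reaching the Table 1 count, as its caption indicates. If crossing required one event more, the bias would be +0.2, +1.7 and +6.4 points at 5%, 10% and 20%. With 2 or 3 patients already on treatment and counted, the excess lower-tail error at 5% essentially disappears, though upward bias remains.

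The result does not show that the boundary stops too often. Section 11.4 gives an erroneous stopping rate of about 1/8; the exact value for Table 1 at a true 5% is 0.074, within that bound.

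**What to change.** In 11.3, keep the raw x/N and its exact 95% interval, and label both as unadjusted for the 11.4 stopping rule. Beside them, add an exact 95% interval by stage-wise ordering of the Table 1 stopping points, with one adjusted point estimate named in advance: the median-unbiased estimate, which reduces mean bias at true rates of 10% to 20% but does not remove it, or the UMVUE, which is mean-unbiased. Compute these at the boundary crossing, and report separately the outcomes of patients already on treatment then, because stage-wise ordering over the exact stopping points does not cover them. State that any comparison with the 5% and 20% benchmarks uses the adjusted interval.

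The cost is a few sentences in the SAP and an enumeration of 37 end points; no patients or data are added, and Table 1 is unchanged. The drawback is that the adjusted estimate after an early safety stop is lower than the raw rate. Showing both, and choosing the estimator before results are known, keeps that from looking like a selective reading.

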The association between responses (e.g. response, progression free and overall survival) and baseline laboratory parameters (e.g. CD4+, CD4+/Foxp3, CD8+, Ki 67, Tumor) will be summarized graphically (boxplots, scatterplots, Kaplan-Meier curves) and numerically (means, medians). For binary outcomes such as response, logistic regression will be used to assess the significance of associations individually (univariate) and while adjusting for other variables (multivariate). The Cox proportional hazards model will be used to model the effect of these

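### The response models in section 11.3 will rest on about 7 to 14 responders, so ordinary logistic regression would overstate odds ratios on average; Firth penalized regression is a cheap improvement

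*Combined protocol and SAP*

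**What the plan says.** Section 11.3, Secondary Objectives, plans to relate response to baseline markers by logistic regression: "logistic regression will be used to assess the significance of associations individually (univariate) and while adjusting for other variables (multivariate". The candidate predictors are given as examples: "baseline laboratory parameters (e.g. CD4+, CD4+/Foxp3, CD8+, Ki 67, Tumor". The text does not name the estimator, the test (Wald, score or likelihood ratio), a significance level for these tests or the number of covariates per model. No penalized or exact method appears anywhere in the document. The one condition about having enough responders, under the Treg and PET analyses in the same section, governs a three-group ANOVA and not the logistic models.

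The amount of information is set by the Primary Objective of section 11.3: "the cohort will be expanded so that 36 new patients will be treated at this dose level". The lower design response rate is stated as "The combination treatment will be considered unsuccessful if the response rate is 20% or less". The upper one, at which the treatment would merit further study, is 40%.

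The marker analysis serves secondary objective 1.3.4. No decision rule is attached to it.

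**The concern.** The precision of a logistic model depends on the smaller outcome group, here the responders. With few responders per covariate, maximum-likelihood coefficients are biased away from zero, the chi-square reference for the likelihood-ratio test becomes too liberal, and in some data sets a covariate combination separates responders from non-responders so that no finite estimate exists. The purpose of the analysis is to identify markers of response to the combination. An adjusted odds ratio that is too large on average could be carried into the design of a later study. The plan also has no fallback for a model that does not converge.

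**Working it through.** **Inputs from the plan (section 11.3, Primary Objective).** n = 36; null rate 20%; target rate 40%; the null is rejected "If 11 or more of the patients have a response". The plan states "This design has type I and type II errors of 0.09 and 0.09, respectively".

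**The plan's own figure reproduces.** Exact binomial, n = 36, threshold 11: P(X ≥ 11 | 0.20) = 0.0889 and P(X ≥ 11 | 0.40) = 0.9096, so the type II error is 0.0904. Both round to 0.09. No smaller n meets both 10% limits.

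**Expected responders.** 36 × 0.20 = 7.2 and 36 × 0.40 = 14.4. If all five example markers entered one model, that gives 7.2/5 = 1.4 to 14.4/5 = 2.9 responders per covariate. Missing marker samples would lower this.

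**Assumptions, because the plan is silent.** Standard normal covariates with pairwise correlation 0.3; 1, 3 or 5 covariates; a log odds ratio for the tested covariate of 0 or ln 2 = 0.693 per SD; two-sided 5% tests; response rates 20%, 30% and 40%; 3,000 data sets of 36 patients per setting.

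**Methods compared.** Maximum likelihood maximises l(β). Its likelihood-ratio statistic is 2{l(full) − l(tested coefficient = 0)}, and its Wald statistic is the estimate over its standard error. Firth maximises l*(β) = l(β) + ½ log|I(β)|, where I is the information matrix, and tests with 2{l*(full) − l*(tested coefficient = 0)}.

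**Estimates when the true log odds ratio is 0.693** (each cell: 20% / 30% / 40% response; maximum-likelihood means exclude separated fits)

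| Covariates | ML mean | ML mean as OR | ML median | Firth mean |
|---|---|---|---|---|
| 1 | 0.818 / 0.788 / 0.778 | 2.3 / 2.2 / 2.2 | 0.750 / 0.738 / 0.723 | 0.702 / 0.694 / 0.693 |
| 3 | 0.914 / 0.878 / 0.847 | 2.5 / 2.4 / 2.3 | 0.787 / 0.801 / 0.776 | 0.710 / 0.711 / 0.703 |
| 5 | 1.005 / 0.997 / 0.936 | 2.7 / 2.7 / 2.5 | 0.876 / 0.853 / 0.833 | 0.701 / 0.730 / 0.713 |

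With five covariates the mean bias on the log scale is (0.936 − 0.693)/0.693 = 35% to (1.005 − 0.693)/0.693 = 45%. The ML medians correspond to odds ratios of 2.3 to 2.4. Firth corrects the mean; its medians with five covariates are slightly low, at 0.64 to 0.66.

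**Rejection rate when the true log odds ratio is 0** (nominal 5%)

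| Covariates | ML likelihood ratio | ML Wald | Firth penalized likelihood ratio |
|---|---|---|---|
| 1 | 5.8 / 6.3 / 5.4% | 2.8 / 3.7 / 3.2% | 3.9 / 4.8 / 4.1% |
| 3 | 7.0 / 6.6 / 7.2% | 3.3 / 3.8 / 4.6% | 4.3 / 4.3 / 5.1% |
| 5 | 9.2 / 7.8 / 8.3% | 3.2 / 4.1 / 5.1% | 4.3 / 4.4 / 5.1% |

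The Monte Carlo standard error near 5% is √(0.05 × 0.95/3000) = 0.4 percentage points, so the one-covariate inflation is small. With responders fixed at exactly 7 or exactly 14 and five covariates, the likelihood-ratio error is 8.2% in both cases, against 4.3% and 5.0% for Firth.

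**Separation.** With five covariates and a true odds ratio of 2.0, 3.1% of maximum-likelihood fits separate at 20% response, 0.3% at 30% and 0.1% at 40%. With 7 responders, five covariates and a binary tested covariate (no true effect) it is 7.7%.

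**Robustness.** A separate simulation of the same kind gave mean ML log odds ratios of 0.91–0.98, 0.82–0.90 and 0.77–0.82 with 5, 3 and 1 covariates, Firth means of 0.68–0.71, and likelihood-ratio and Wald errors of 6–8% and 3–6%.

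**The case against.** The strongest reply is that the plan does not commit to what is criticised. A reader might infer that the analysis as written will flag null markers too often. The documents do not support that: no likelihood-ratio test is named, and Wald tests hold their level. What remains under Wald is the bias in the estimates.

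A reader might also infer that all five markers go into a single model. The list is introduced as examples, univariate models are named alongside multivariate ones, and no model size is fixed. In univariate models the bias is modest (12% to 18% of the mean log odds ratio) and the likelihood-ratio error is close to nominal.

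Thirdly, Firth may be taken as a remedy for unreliable marker findings in general. It is not. Among significant results with a true odds ratio of 2.0 and five covariates, a further simulation gave a mean Firth log odds ratio of 1.21 to 1.56 (OR 3.4 to 4.8), against 1.51 to 2.13 by maximum likelihood. Firth's power for that effect is only 22% to 34%. Capping the number of covariates would act on the cause more directly. This objection stands and limits what the change can be said to achieve.

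Finally, the consequence is limited. The primary exact binomial test is untouched, and the specifically hypothesised Treg and PET markers are also to be examined by t tests and by sensitivity and specificity, which do not depend on the logistic fit.

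**Conclusion.** The point holds as a minor, inexpensive improvement to a secondary analysis. If logistic regression means maximum likelihood, which is the default reading though not stated, odds ratios will be too large on average: for a true value of 2.0, about 2.5 to 2.7 with five covariates, 2.3 to 2.5 with three and 2.2 to 2.3 with one. The typical (median) overstatement is smaller, and a small share of fits will separate. Inflation of false positives is conditional on likelihood-ratio tests being used: about 7% to 9% with three to five covariates, 5% to 6% with one. These sizes rest on assumed covariate distributions, correlation and model size, and on complete marker data in 36 patients. The direction of the bias was the same in every setting tried.

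**What to change.** In section 11.3, state that the models for response, above all the multivariable ones, will be fitted by Firth penalized logistic regression, with tests and confidence intervals from the profile penalized likelihood. Wald tests should not be paired with Firth estimates: in the same simulations they rejected a null marker in only 1.4% to 2.4% of data sets. State also that these results are exploratory, since the change does not deal with selection for significance, multiplicity or low power.

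The cost is SAP wording. The method is in standard software, and no change to sample size, data collection or conduct is needed. Relative to maximum-likelihood likelihood-ratio tests, fewer results will be nominally significant: with five covariates and a true odds ratio of 2.0, the rejection rate falls from 34% to 22% at 20% response and from 43% to 34% at 40%. Part of that loss is the removal of the excess error.

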**NCI Protocol #: 7870**

parameters on time-to-event outcomes.

Logistic regression will be used to explore the relationship between entinostat exposure (plasma concentrations) with pharmacodynamic (PD) endpoints (e.g., toxicity and histone acetylation in peripheral blood mononuclear cells and change in T cell subset population).

We will determine if initial levels of specific T lymphocytes (Tregs) or changes in the level of specific T lymphocytes from baseline might predict for response to this combination therapy. In this study Tregs are defined as CD4+CD25hi T cells. The hypotheses are that low baseline levels of Treg would be associated with an increased probability of response and that decreasing Tregs from baseline would be associated with an increased probability of response. Continuous baseline values of Treg (expressed as a frequency) and the change in Treg from baseline (4 weeks post treatment – pretreatment) as well as binary versions of these variables will be explored for an association with response. A 30% decrease from baseline will be used as the binary cutpoint for Treg change.

Two PET-derived indices of glucose metabolism: Standard Uptake Value (SUV) and FDG influx rate constant (Ki) will be used to determine whether early changes in tumor metabolisms by FDG PET/CT scan anticipate anatomic changes in patients receiving the combination of entinostat and IL-2. These two parameters will be measured at baseline and at week 5 using identical PET/CT acquisition protocols. Continuous change from baseline and binary (30% decrease from baseline) measures of these predictors will also be explored for an association with response. The hypothesis for these predictors is that treatment would decrease glucose metabolism, increasing response.

Data analysis for Treg and PET correlative studies:

This study will provide estimates of means and standard deviations for baseline Treg, change in Treg at week four and changes in the PET glucose metabolism indices at week five. Transformations of these predictors will be considered before analyses. For each endpoint, we will determine how well the responders and non-responders are distinguished. For binary predictors, the sensitivity and specificity with 95% confidence intervals will be reported. T tests will be used to compare the mean change between responders and non-responders. If there are sufficient numbers of responders, partial responders and non-responders an ANOVA will be used to compare changes in these three groups. If complete data are obtained for CD4+CD25hi T cells at multiple time points post treatment, repeated measures ANOVA will be performed to evaluate data for trends over time.

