### 1.3 Phase II Secondary Objectives

1.3.1 To compare the time-to-tumor progression, progression-free survival and overall survival of patients with metastatic RCC treated with high dose aldesleukin combined with entinostat to the historical data of patients treated with high dose aldesleukin alone.

1.3.2 To assess the toxicity of high dose aldesleukin combined with entinostat.

1.3.3 To evaluate entinostat pharmacodynamics (PD) in blood and tumor samples.

1.3.4 To measure the association between baseline laboratory parameters (e.g. CD4+, CD8+, CD4+/Foxp3), tumor blood metabolism, and a variety of response variables (e.g. toxicity, response and survival).

1.3.5 To explore the relationship between entinostat exposure with PD endpoints (e.g. toxicity and histone acetylation in peripheral blood mononuclear cells or PBMNCs and changes in T cell subset population).

1.3.6 To evaluate the modulation of tumor metabolism by FDG PET/CT scan.

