#### Dosing levels

Dose Level	Entinostat (mg, every 2 weeks, PO)	Aldesleukin (IU/kg, every 8hrs, IV)
0	1	600,000
1	3	600,000
2	5	600,000

Patients will receive only entinostat during the “maintenance” (between cycles) period. During Phase II, patients receiving 5 mg entinostat during the “maintenance” period will be given the option to dose escalate entinostat to 10 mg PO if tolerated except two weeks before and two weeks after administration of aldesleukin.

The recommended dose of 5 mg PO every 2 weeks was determined in the Phase I portion of the study. This cohort will be expanded in the phase II portion so that 36 new patients will be treated at this dose level. The evaluations for the phase II component of the study will be identical to the phase I portion.

Compliance will be assessed via patient diaries Also, pill containers will be returned to the study doctor or nurse at the end of each cycle.

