## 7. CORRELATIVE/SPECIAL STUDIES

### 7.1 Pharmacodynamic Studies

#### **PBMCs:**

Relationships between entinostat and aldesleukin exposure and pharmacodynamic effects (e.g. histone acetylation in peripheral blood mononuclear cells or PBMCs and changes in T cell subset population) will be characterized.

Collect four 8 ml of peripheral blood in CPT tubes for mononuclear cell fraction. Mononuclear cell fractions will be obtained in CPT tubes (Beckon Dickinson) sodium citrate using manufacture's guidelines.

Collection time points will be:

- Prior to treatment on Day -14 and Day-7,
- Cycle 1 – pre-dose on Day 1 and at 8 hrs. and 24 hrs. after the dose of entinostat,
- Cycle 1 - pre-dose Day 15
- Cycle 2 and 3 - pre-dose Day 1
- Cycle 2 and 3 - pre-dose Day 15
- At the time of progression.

Samples will be processed, PBMCs isolated and histone acetylation status determined. Blood samples will be also analyzed for immune cell sub populations. CD4+, CD4+/Foxp3, CD8+ cells, NK cells will be quantitated by FACS analysis. Foxp3 gene expression will be evaluated by quantitative RTPCR. Specimens must be shipped at ambient temperature.

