## **7.2 Pharmacokinetic studies (Phase I only)**

Pharmacokinetic analysis will be performed by [name], PhD. at the Analytical Pharmacology Core Laboratory at the SKCCC at Johns Hopkins. Patients in the phase I component of the study will have plasma samples collected to assess entinostat pharmacokinetics. Entinostat concentrations will be assessed pretreatment on Day -14 and at 2 and 6 hrs., Day -7, pretreatment on Day 1 and at 2 and 6 hrs. and Day 15 during the first cycle and at the time of progression. These pharmacokinetic parameters will be used to explore the relationship between entinostat exposure with pharmacodynamic (PD) endpoints such as toxicity and histone acetylation in peripheral blood mononuclear cells or PBMCs and changes in T cell subset populations.

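### Section 11.3 names only logistic regression for relating entinostat concentration to pharmacodynamic endpoints, although T-cell change is quantitative and plasma sampling is planned in Phase I only

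*Combined protocol and SAP*

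**What the plan says.** Objective 1.3.5, under the Phase II secondary objectives, is "To explore the relationship between entinostat exposure with PD endpoints". Its analysis is in section 11.3 (Phase II), where one method is named: "Logistic regression will be used to explore the relationship between entinostat exposure (plasma concentrations) with pharmacodynamic (PD) endpoints". The endpoints given as examples are "toxicity and histone acetylation in peripheral blood mononuclear cells and change in T cell subset population".

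On measurement, section 7.1 says of the T-cell populations: "CD4+, CD4+/Foxp3, CD8+ cells, NK cells will be quantitated by FACS analysis". For histones it says only: "Samples will be processed, PBMCs isolated and histone acetylation status determined".

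On sampling, the heading of section 7.2 restricts pharmacokinetics to Phase I, and its text says: "Patients in the phase I component of the study will have plasma samples collected to assess entinostat pharmacokinetics". The same section adds that these results will be related to pharmacodynamic endpoints. The text under the dosing-level table in section 4.1 says: "The evaluations for the phase II component of the study will be identical to the phase I portion". The study calendar (section 8) has rows for pharmacodynamic and microRNA samples and none for pharmacokinetics in either phase.

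**The concern.** Logistic regression needs a binary outcome, and section 11.3 itself introduces it, a little earlier, for binary outcomes such as response. Toxicity can be binary. A FACS measurement of T-cell change is not, unless someone chooses a threshold, and the plan gives none for this use. A threshold chosen after seeing a few patients is open to selection. It also discards information, and small logistic fits may give no finite estimate.

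Separately, a reader of 1.3.5 and 11.3 would expect an exposure analysis in the 36 Phase II patients. Section 7.2 plans no concentrations for them, while section 4.1 can be read as requiring the same draws as in Phase I. Sites and analysts could act on different readings.

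**Working it through.** **Plan's own figures.** The plan gives no sample size, power or cut-point for this analysis. The only related figure is the 36 Phase II patients. The rule of 11 or more responses in 36 (20% against 40%) reproduces: exact binomial type I error 0.0889 and type II error 0.0904, both stated as 0.09. It serves here only as the count of patients with no planned concentrations.

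**Method against endpoint.**

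| Endpoint | Scale in the plan | Cut-point as an outcome of exposure | Logistic regression fits? |
|---|---|---|---|
| Toxicity | can be binary | not needed if defined as yes/no | yes |
| T-cell subset change | quantitative (FACS, 7.1) | none | only after a split |
| Histone acetylation | not stated (a *status*, 7.1) | none | cannot be judged |

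The 30% decrease for Treg change in section 11.3 is a cut-point for Treg change as a predictor of tumour response. It does not define an outcome of exposure, and it does not cover CD8+ or NK cells.

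**Patients with concentrations (inferred).** Section 4.1 reports that 5 mg, dose level 2, was selected. Under sections 4.1 and 11.2, level 2 opens only if level 1 has no DLT.
- Level 1: a minimum of 3; I assume 3 to 4.
- Level 2: 3 or 4, plus 3 or 4 more after one DLT (section 11.2), so 3 to 8.
- Total: 3 + 3 = 6 up to 4 + 8 = 12. Replacement of non-evaluable patients (section 11.7.2) could shift this slightly.
- Phase II: 0 of 36 planned.

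**Information kept by a split (illustrative, large-sample, normal outcome).** With a proportion p below the cut, relative efficiency = φ(z_p)² / [p(1 − p)].
- p = 0.5: 2/π = 0.64
- p = 0.3: 0.58
- p = 0.2: 0.49
- p = 0.1: 0.34

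At the median split, 6 patients carry the information of about 6 × 0.64 = 3.8, and 12 that of about 12 × 0.64 = 7.7.

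**Estimability.** I simulated one normal exposure and one normal endpoint per patient, with an assumed correlation of 0.7. The share of data sets with no finite logistic estimate was:

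| n | Cut fixed at the population median | Split at the sample median |
|---|---|---|
| 6 | 46% | 30% |
| 8 | 28% | 19% |
| 12 | 11% | 7% |

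Power comparisons depend on how such fits are counted. The lower logistic figure below counts them as non-significant. The upper adds all of them as significant (fixed cut, two-sided 5%, likelihood-ratio test).

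| n | Linear | Logistic, lower | Logistic, upper |
|---|---|---|---|
| 6 | 0.38 | 0.04 | 0.04 + 0.46 = 0.50 |
| 8 | 0.57 | 0.21 | about 0.21 + 0.28 = 0.49 |
| 12 | 0.76 | 0.50 | 0.50 + 0.11 = 0.61 |

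Linear regression is ahead on either count at 8 and 12. At 6 the ordering depends on the counting, so I draw no power conclusion there.

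**Toxicity.** If toxicity means DLT, selecting 5 mg under the section 11.2 rules implies none at level 1 and at most one at level 2. Ordinary logistic regression is then fragile even where the outcome is binary.

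**The case against.** The best reply is that the sentence says *explore*, that no alpha, power or decision hangs on it, and that logistic regression suits toxicity, the first endpoint listed. All of that stands and sets the severity. It does not supply a model for T-cell change.

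Four stronger readings are tempting, and the documents do not support them.
- A reader might infer that objective 1.3.5 has no data and cannot be met. Section 7.2 gives the analysis a Phase I source, neither 1.3.5 nor 11.3 limits it to Phase II patients, and pharmacodynamic sampling is not limited to Phase I. Only Phase II concentrations are missing.
- A reader might infer that histone acetylation is continuous and therefore mishandled. The scale is not stated. If it is scored as present or absent, logistic regression would fit, though the scoring would still need a definition.
- A reader might infer a larger Phase I set by allowing both dose levels to expand. With 5 mg selected, the rules exclude expansion of level 1 for a DLT.
- A reader might take the 64% as the loss this trial will incur. The plan mentions no median split, and the figure is a large-sample one for a normal outcome, applied here to a handful of patients.

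It is also fair to say that linear or mixed models in 6 to 12 patients are not robust either, and that a log-concentration model is undefined at a zero concentration. The scheduled pretreatment sample on Day -14 precedes any entinostat, so any replacement method needs a rule for it.

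**Conclusion.** The point holds in limited form. For T-cell change, the only named method does not match the measurement and no cut-point is given. For histone acetylation, the gap is an unstated scale. For toxicity, logistic regression is appropriate in kind. The Phase II placement of 1.3.5 and the statement in section 4.1 that evaluations are identical conflict with Phase I-only sampling in section 7.2, which leaves 0 of 36 Phase II patients with planned concentrations.

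On size, a split keeps at most about 64% of the information under normality, and logistic estimates may not exist in a noticeable share of data sets (7% to 46% in the settings above). These figures rest on assumed normality, a correlation of 0.7 and an inferred 6 to 12 patients; none is in the documents. The analysis is secondary and exploratory, the primary endpoint is untouched, and the change is desirable rather than essential.

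**What to change.** In section 11.3:
- Analyse quantitative endpoints (T-cell change, and histone acetylation if it is measured on a continuous scale) by linear regression or Spearman correlation on post-dose concentration, accounting for repeated samples where the data allow.
- Exclude the pretreatment Day -14 sample, or handle it separately.
- State the scale of histone acetylation, and its definition if it is binary.
- Keep logistic regression for binary toxicity, in exact or Firth form because events will be few.

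In objective 1.3.5 and section 11.3, state that the exposure analysis is exploratory and uses Phase I patients. Reconcile the sentence in section 4.1 with section 7.2. If Phase II plasma sampling was in fact intended, section 7.2 and the calendar would have to say so, and that would add samples.

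The recommended route costs protocol and SAP wording only, with no new samples and no change to the design.
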